We are allowing these treatments for two reasons. First, the subjects in this study will be significantly symptomatic, and it could be impractical or unsafe, and correspondingly unethical, to deny them access to some type of psychosocial intervention for their ongoing symptoms. Second, all subjects will be receiving TAU which may include a combination of treatments including medications, breathing exercises, and talk therapy. While a course of another psychosocial treatment through the PTSD Clinic or the Domiciliary Care Program may provide valuable support and some symptomatic relief, we believe that it is unlikely that one of these treatments would result in a significant magnitude of symptom reduction that would confound the study results. We will require that all non-study treatments be provided through the VA GLA PTSD Clinic or Domiciliary Care Program which will make it possible for us to carefully record any non-study medication or psychosocial treatments that the subjects are receiving for their PTSD. We will use uncontrolled treatment as a covariate in analyses if indicated due to unbalanced frequency or intensity of treatments received between the active and sham TNS groups.

Individuals with Major Depressive Disorder (MDD) will not be excluded if they meet the inclusion and exclusion criteria. MDD often is comorbid with PTSD, so that excluding these

subjects would limit generalizability of results. Individuals with active substance dependence, bipolar or other psychotic disorders, or severe TBI will be excluded because TNS may not work in the same manner or achieve the same degree of effectiveness in such individuals compared with patients who do not have these conditions. In this initial blinded efficacy study, we believe that it is important to eliminate these potential confounds. We do not anticipate that many subjects will be excluded because of bipolar or psychotic disorders because such patients generally have been identified prior to their registration in the PTSD Clinic or Domiciliary Care Program and are being treated elsewhere in the VA GLA. Some patients will have suffered or will suffer from an active substance use disorder, and these subjects will be excluded from the study.

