This is a collaboration between the VA GLA and UCLA. All study activites will will be performed at the VA Greater Los Angeles or UCLA as determined by the Principal Investigator, in consultation with the PTSD Clinic and Domiciliary Care Program directors, as well as the subject's preference. Identification, recruitment and consenting of subjects for participation will be performed at the VA GLA PTSD Clinic or the Domiciliary Care Program. The baseline visit, Week 4 visit, and Week 8 visit will be conducted at the VA GLA PTSD Clinic or Domicialiary Care program without exception. All other study activities and visits will be performed at UCLA, or at the VA GLA PTSD Clinic or Domiciliary Care Program. If subjects prefer that visits be performed at the VA, the clinic director approves such visits, and space is available in the clinic, these visits will be performed at the VA GLA PTSD Clinic or the Domiciliary Care Program. Subjects will be randomized to treatment with either active or sham TNS for a period of eight weeks. Subjects will be randomly assigned in a double-blind manner (n=37 in each group); all subjects and the research staff who interact with them will be blinded to assignment, and a separate UCLA staff member of the research team who has no contact with subjects will program the TNS device settings. Subjects assigned to the sham treatment condition will receive a TNS stimulator that will look identical to the active treatment stimulator, and will follow identical procedures for the use of this stimulator. The sham unit, however, will deliver no actual nerve stimulation (i.e., it will pulse at 0 Hz). It will be explained to all subjects that they may or may not feel any sensation while using the device and any sensations or lack there of is not indicative of which treatment they are receiving. There is no noise associated with the device. The TNS device is equipped with a lighted display which will turn on to indicate to the patient when stimulation is being administered. The display on the sham device will turn on when stimulation is given at 0 Hz to avoid the appearance of a difference between the sham and active treatment.

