Subjects will be followed weekly with ratings of PTSD symptoms, mood and anxiety, as well as examinations for risk of suicidality. Week 8 endpoint measures will include severity and frequency of PTSD symptoms, quality of sleep, and quality of life measures. The primary endpoint measure is the change in symptom severity at the week 8 visit. The week 8 time point will be used to compare changes in symptoms between subjects who were randomly assigned to the active vs. sham TNS treatment condition. Subjects also will be interviewed an additional 4 weeks after the conclusion of the sham controlled treatment, and their mood and anxiety symptoms assessed, to examine the durability of any symptom change that subjects experienced during the initial 8 weeks. At the end of week 8, subject improvement will be assessed and those showing a $\geq 25\%$ improvement from baseline at the end of 8 weeks of treatment will be eligible to participate in the 42-month extension phase to monitor and observe possible benefits of prolonged TNS in responders. Subjects who participate in the extension phase will remain blinded. Subjects complete the PCL-M and BDI monthly during their participation in the extension phase. The PCL-M monthly score determines on-going inclusion in this phase. Subjects will be withdrawn in the case of adverse events, or symptom worsening (quantified as > 25%worsening in symptoms after one month as compared to the beginning of the extension phase as assessed using the PCL-M total score). Subjects way also voluntarily withdraw from the extension phase at any time.

Subjects who do not participate in the extension phase will be unblinded and told whether they received the active or sham-controlled treatment after all study and follow-up visits have been completed. This includes completion of the eight-week double-blind treatment phase and four-week follow-up phase for a total of 12 weeks in this study. Data will be examined for differences

between active and sham treatment, as well as safety and acceptability of the treatment. If positive, this preliminary study will serve as the basis for a larger pivotal trial of effectiveness.

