Screening Procedures and Instruments: After signing the consent form, the research coordinator will interview subjects to ask about demographic data and assess for possible exclusion criteria. The instruments listed below will be used to determine eligibility for the study and assess symptom severity. Instruments will be administered on the schedule shown in Table 1 below. Clinician-Administered PTSD Scale for DSM-V (CAPS-5-5) (Blake et al., 1995; Weathers et al., 2001): The CAPS-5 will be used both to establish eligibility for inclusion in the protocol and as an outcome measure. This 30-item structured interview assesses the presence, frequency, and severity of symptoms of PTSD. It provides a continuous score of frequency and severity for each symptom, with overall severity characterized by summing the total score for the individual items. The CAPS-5 has good psychometric properties across a wide variety of clinical populations and research settings (Weathers et al., 2001). We first will determine using the CAPS-5-5 whether the subject has at least one Criterion A stressor related to warzone exposure. If the subject meets this criterion, the remainder of the CAPS-5-5 will be administered to confirm the presence of PTSD and assess severity. Frequency and severity of symptoms are rated separately on a 0-4 scale.

Mini International Neuropsychiatric Interview for DSM-IV, Version 5.0 (MINI) (Sheehan et al.,1998): The MINI is a short yet accurate structured diagnostic interview used to diagnose current and lifetime Axis I disorders according to DSM-IV criteria. The assessment takes approximately 15 minutes to administer (Sheehan et al., 1998) We will specifically assess current substance dependence, current and/or history of psychosis, bipolar disorder, and to assess possible presence of exclusion criteria through use of relevant modules from the MINI. We also will utilize this instrument to determine the presence of Major Depressive Disorder (MDD); subjects will not be ruled-out because of the presence of MDD, but the presence of the illness will be used as a covariate. If presence of MDD appears to affect outcome, we may perform a subgroup analysis in subjects with comorbid MDD.

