Following the baseline assessment, subjects then will be randomized to one of the two treatment conditions. Treatment assignment will be randomized within cells defined by gender, symptom severity, and presence of current medication treatment to provide a degree of balance on key underlying characteristics that otherwise would have the potential to confound the interpretation of study findings. Specifically, there will be eight strata for randomization defined by the 2 x 2 x 2 combinations of gender (male or female), symptom severity (lower or higher defined by whether the CAPS-5 score on entry is less than 78, the median value for this sample, versus being 78 or greater), and presence of current medication treatment (yes or no). Within these strata, randomization will occur in blocks of two, so that after every two patients with a given combination of stratum-defining characteristics, there will be one patient assigned to the active intervention and one to the control arm. The randomization will be carried out by associating strata with rows of the random-number table in Cochran (1977, p. 19). For the first member of each successive pair of patients presenting with a given set of stratum-defining characteristics, if the next number in the row is in the range of 5 through 9, then the patient will be assigned the active intervention, else the patient will be assigned to the sham. If the first subject was assigned the active intervention, then the next subject would be assigned the sham, and vice versa; for the next subject after that, the random-number table will be used in the same way. The pairing in the design could be considered in the analysis, and we will plan to do so using a permutation-test approach for purposes of being complete. The core motivation for the pairing, however, is to ensure that treatment assignment remains balanced across arms rather than because we believe that there is anything scientifically important about whether the subject arrives at an odd or an even number in the sequence. For our primary analysis, we will use a randomized-block ANOVA that accounts for the 2 x 2 x 2 stratification in the design but does not reduce the error degrees of freedom on account of the pairing.

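### The optional MDD subgroup analysis is triggered by whether MDD affects outcome, which is an unreliable signal of whether TNS works differently in MDD, and an MDD-only result cannot show who benefits

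*Combined protocol and SAP*

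**What the plan says.** Section 12 (Eligibility Screening) admits subjects with comorbid depression: "Individuals with Major Depressive Disorder (MDD) will not be excluded if they meet the inclusion and exclusion criteria". The expected share is not given.

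Section 13, Screening Procedures and Instruments, under the MINI, gives MDD two roles. The first is adjustment: "subjects will not be ruled-out because of the presence of MDD, but the presence of the illness will be used as a covariate". The second follows at once: "If presence of MDD appears to affect outcome, we may perform a subgroup analysis in subjects with comorbid MDD". No test or threshold defines the condition, and the analysis is optional.

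Section 13, Conduct of the study, stratifies randomization by gender, CAPS-5 severity and current medication, not by MDD. On the analysis it says: "For our primary analysis, we will use a randomized-block ANOVA that accounts for the 2 x 2 x 2 stratification in the design". It does not mention MDD.

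The Overview of section 13 defines the endpoint: "The primary endpoint measure is the change in symptom severity at the week 8 visit". It gives 74 subjects, 37 per arm.

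The available text contains no treatment-by-MDD interaction, no matching estimate in subjects without MDD, and no label marking this subgroup analysis as exploratory.

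**The concern.** Two questions are being run together. One is whether subjects with MDD do better or worse on average (prognosis). The other is whether the active-minus-sham difference depends on MDD (effect modification). The sentence tests the first and then acts as though it bore on the second.

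The analysis it opens also lacks a comparator. A significant result in MDD subjects does not show that TNS works better in them, because subjects without MDD may benefit equally. A non-significant result does not show that TNS fails in them, because the subgroup is small. Since the condition has no threshold, the decision to proceed is made after outcomes are seen.

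What is at stake is the reading of who benefits. The open-label PTSD pilot in section 16 enrolled only adults with PTSD and comorbid MDD, so an MDD-only finding could look like confirmation. The Overview says that a positive result would be the basis for a larger pivotal trial, whose population could be shaped by that reading.

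**Working it through.** The plan states no figure on this point, so there is none to reproduce. What follows is an illustration.

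**Inputs from the documents:** 37 per arm, 1:1 allocation, MDD allowed, MDD not a stratification factor.

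**Assumptions:** 18 MDD and 19 non-MDD subjects per arm; outcome SD 1, scored so that higher is better; two-sided 5% tests; the trigger read as an MDD main effect with p<0.05. Effect sizes are illustrative.

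**Step 1: what the trigger measures.** With 1:1 allocation, the expected MDD main effect is

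prognostic offset + ½ × (TNS effect in MDD − TNS effect in non-MDD).

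It mixes the two quantities, and they can cancel.

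**Step 2: standard errors.**
- Interaction: √(2/18 + 2/19) = 0.465.
- MDD main effect: half of that, 0.233.

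**Step 3: approximate rates by formula.**
- MDD 0.5 SD worse, same TNS effect in both groups: the trigger fires with probability Φ(0.5/0.233 − 1.96) = Φ(0.19) ≈ 0.57. The interaction test rejects in 5%, as it should.
- TNS effect 0.65 SD in MDD and 0 otherwise, offset −0.325: expected main effect −0.325 + ½ × 0.65 = 0, so the trigger fires at its 5% error rate. Interaction test: Φ(0.65/0.465 − 1.96) = Φ(−0.56) ≈ 0.29.
- TNS effect 1.0 SD in MDD and 0 otherwise, offset −0.5: expected main effect again 0. Interaction test: Φ(1.0/0.465 − 1.96) ≈ 0.57.

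**Step 4: simulation with t tests (20,000 or more trials per row).**

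| Offset for MDD | TNS effect, MDD / non-MDD | Trigger fires | Interaction test rejects |
|---|---|---|---|
| −0.5 | 0.65 / 0.65 | 56% | 5% |
| −0.8 | 0.65 / 0.65 | 92% | 5% |
| −0.325 | 0.65 / 0 | 5% | 28% |
| −0.5 | 1.0 / 0 | 4-5% | 56% |
| 0 | 0.65 / 0 | 28% | 28% |

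In the first two rows, where the benefit is the same for everyone, the MDD-only comparison that follows the trigger is significant about 48% of the time. It misses that benefit in about half of the triggered trials. A 0.65 SD effect has about 80% power in the full sample.

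**Step 5: false positives with no TNS effect.** Suppose benefit is claimed if either the overall test or the triggered MDD-only test is significant. The chance of at least one false positive is about 5% when MDD is not prognostic, about 7% with an offset of 0.5 SD, and about 8% with 0.8 SD. Varying the MDD share from 40% to 60% changes this little.

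**Step 6: what the better test can detect.** At 80% power the detectable interaction is 2.80 × 0.465 = 1.30 SD. With 30% or 70% MDD the standard error is √(2/11.1 + 2/25.9) = 0.507. The detectable interaction is then 1.42 SD, and power for 0.65 SD is about 25%.

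**The case against.** The analysis is optional and secondary, in a study that calls itself preliminary. Nothing in the plan says that a subgroup p value would support a claim, and the pilot population is a fair scientific reason to look at MDD. The wording may also have been meant as an effect on response to TNS. These points stand as limits on the seriousness of the issue. They do not repair the rule: the condition follows directly on MDD as a covariate, and no treatment-by-MDD term is named.

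Three stronger readings are tempting, and the documents do not support them.

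- A reader might infer that the rule raises the false-positive rate to 8-9%. That is the result if the MDD-only test is always run. The plan makes it conditional and optional, so the range is about 5% to 8%, with the top reached only if the trigger nearly always fires. A still higher figure that adds a non-MDD test would describe an analysis nobody planned.
- A reader might infer that an association of MDD with outcome carries no information about effect modification. The last row of the table shows otherwise: without a prognostic offset, the trigger does as well as the interaction test. It is unreliable, not empty.
- A reader might infer that the covariate statement and the primary ANOVA contradict each other. The ANOVA sentence does not list every term and does not rule out covariates, so the two can be read together. What is unclear is which model carries MDD.

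**Conclusion.** The concern holds as a minor point about interpretation. The trigger tests prognosis, and the MDD-only analysis cannot separate a benefit specific to MDD from one shared by all. Under the stated assumptions the trigger fires in about 56% of trials when nothing about the TNS effect differs, and in about 4-5% when it differs but prognosis masks the difference, against 28-56% for an interaction test. Any inflation of false-positive claims is modest, at most about 8%, and arises only if the subgroup result is used to claim benefit.

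The exact percentages depend on the assumed MDD share, effect sizes and p<0.05 reading of the trigger, none of which the documents give. That the trigger mixes prognosis with effect modification follows from the expression in step 1 and does not depend on them.

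**What to change.** Delete the outcome-based trigger and replace it with the following:

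- Pre-specify a separate exploratory model with a treatment-by-MDD term, using MDD status from the baseline MINI.
- Whatever the result, report the interaction estimate with its 95% CI, and the active-minus-sham effect with 95% CI in both MDD and non-MDD subjects.
- State that no claim will rest on a within-subgroup p value.
- Take the primary treatment effect from the model without the interaction. With 0/1 coding, adding the interaction there would turn the treatment coefficient into the effect in one MDD group.
- State whether the MDD covariate named under the MINI enters the primary randomized-block ANOVA as a main effect.

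The cost is a few sentences in the plan and one additional model. The MINI is already scheduled at baseline, so sample size, visits and data collection do not change. The downside is low power: about 28% for a 0.65 SD interaction, with about 1.3 SD detectable at 80% power if half have MDD. The plan should say this, so that a non-significant interaction is not read as evidence of equal benefit.
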